4.2 Study Outcome Measures

4.2.1 Primary Outcome Measures

The primary outcome is the correlation in estimated BAL as measured by the breathalyzer and the wristwatch sensor during the second alcohol self-administration trial. BAL and wristwatch sensor data correlation will be analyzed by repeated measures correlation (rmcorr) analysis, as described in more detail in section 12.

4.2.2 Secondary Outcome Measures

In addition to the determination of correlation between BAL and transdermal alcohol concentration (TAC) as measured by a reference breathalyzer and the developmental KWJ wrist device, respectively, we anticipate that Phase I of this study (the first alcohol self administration trial) will provide a means to determine the characteristic time lag between BAL and TAC [12] and furthermore allow development of a preliminary model for correcting TAC measurements for this lag.

5 Study Design

Calibration Study of a Wearable Noninvasive Blood Alcohol Monitor

Final V1.8 4.24.19

This is a device calibration study designed for healthy non-treatment-seeking drinkers. The drinking lab portion of this study is an adaptation of an established human laboratory self-administration procedures [13]. Subjects who consent to this study will complete two alcohol self-administration sessions, one in the Calibration phase (Phase I) of the study and one in the Validation phase (Phase II) of the study.

Calibration Phase I. The calibration phase of this study is designed to gather data to assist in developing an equation to account for the lag in TAC readings and transform these readings into an approximation of alcohol breath readings. In this calibration phase subjects will be given a measured dose of alcohol to achieve a peak BAL level of 0.05 g/dL after a one hour drinking session. The volume of alcohol will be calculated using an online tool developed by UW-Madison (<http://dionysus.psych.wisc.edu/WebCMS/baccalc.htm>) based on a formula described by Watson [14]. The hour-long drinking session will be followed by a five hour observation period to ensure that subject reach peak TAC. Blood alcohol level will be measured simultaneously using the transdermal sensors and the breathalyzer for the duration of the drinking period and observation period. Breathalyzer readings will be taken every 15 minutes during the entire experiment and transdermal sensors will log data continuously. To ensure residual alcohol in subjects' mouths does not provide a false breath alcohol reading, subjects will rinse their mouth twice with water after consuming a saltine cracker prior to each breathalyzer given while the subject is consuming alcohol. Subjects will remain in the drinking lab for up to five hours to allow for measurement of the peak transdermal alcohol concentration. Given the length of observation, we estimate that subjects will fully metabolize the alcohol they received during the calibration session and they will have a BAL of 0.00 g/dL when the calibration session is over. In the event that a drinking session is halted or the subject has a very slow rate of metabolism, we require that subjects remain in the laboratory until their BAL, as measured by breathalyzer, reaches 0.04 g/dL or less. The drinking session will be video-recorded to provide a record of the exact timing of breathalyzer readings. If methodology or safety issues are uncovered during the Phase I of this study, the protocol may be amended to address these issues prior to completing Phase II.

Validation Phase II. Data from Phase I of this study will be used to develop a model to account for the lag in transdermal sensor readings relative to breathalyzer readings. Once all subjects have completed Phase I and the calibration model is complete, subjects will return to the laboratory to complete Phase II of the study. Given the expected time lag between Phase I and Phase II, eligibility will be re-assessed prior to the Phase II drinking session to ensure subject safety (see appendix A for schedule of events). If the subject remains eligible for Phase II of the study, the Phase II validation drinking session will be scheduled within 14 days of re-assessing eligibility. During the validation drinking session subjects will be given a measured dose of alcohol to achieve a peak BAL level of 0.05 g/dL after a one hour drinking session. The drinking period will be followed by a three-hour observation period. Blood alcohol level will be measured simultaneously using the transdermal sensors and the breathalyzer for the duration of the drinking period and observation period. Breathalyzer readings will be taken every 15 minutes during the entire experiment and transdermal sensors will log data continuously. To ensure residual alcohol in subjects' mouths does not provide a false breath alcohol reading, subjects will rinse their mouth twice with water after consuming a saltine cracker prior to each

Calibration Study of a Wearable Noninvasive Blood Alcohol Monitor

Final V1.8 4.24.19

breathalyzer given during the drinking period. Subjects will remain in the laboratory until their BAL, as measured by breathalyzer, reaches 0.04 g/dL or less.

Subjects: Subjects will be recruited through radio advertisements, newspaper advertisements, study flyers, social media, and internet postings. Interested subjects will be screened by telephone to determine initial eligibility prior to the baseline assessment.

6 Potential Risks and Benefits

6.1 Risks

Physical discomforts:

The drawing of blood may cause pain, bruising, lightheadedness, and on rare occasions, infection. Subjects may briefly feel the prick of the needle when it is inserted. Subjects may feel dizzy or faint when blood is drawn. Trained phlebotomists will be used to minimize these risks.

ECGs may cause discomfort and/or irritation of the skin (redness and itching) from the adhesive electrodes. Hair on the subjects' chest may need to be removed in order to obtain the best electrical contact between the adhesive electrodes and subjects' skin. Trained staff will be used to minimize these risks.

Risk to recovery efforts

Treatment-seeking drinkers will be excluded from this study to minimize the risk that drinking in the laboratory could worsen outcomes for a subject trying to reduce or abstain from alcohol. All subjects will undergo a medical screening and we will exclude subjects who have a medical or mental condition for which alcohol exposure in this study would be contraindicated. All subjects will receive the NIAAA self-help guide *Rethinking Drinking* at the end of study participation [15].

Risk of overconsumption

To minimize the risk of subjects reaching a level of intoxication that is uncomfortable to them, we will remind subjects that they may discontinue study participation at any time. Subjects who qualify for this study will have experience consuming alcohol at an amount similar to the dose chosen for this study. Subjects will be monitored during the course of the study. Medical staff will evaluate subjects and may make a determination to halt study participation if the subject becomes too behaviorally impaired or if there are emergent safety issues. During the descending BAL period, subjects will have access to a comfortable space with entertainment (streaming media), snacks, non-alcoholic beverages, and a nearby bathroom.

Subject release:

- Subjects who have a BAL greater than .04 g/dl or who appear to be too behaviorally impaired to leave our research center will be asked to remain in the clinic until their

Calibration Study of a Wearable Noninvasive Blood Alcohol Monitor

Final V1.8 4.24.19

intoxication is reduced to a level that it is safe to discharge them from the research laboratory.

- Subjects will not be released within 60 minutes of their last drink consumed to ensure that peak BAC has been reached prior to discharge.
- Onsite medical supervision (study RN or GCRU RN) will be maintained while the subjects are in the lab until the time of discharge (<0.040 g/dL) or until they reach a BAL = 0.000 g/dL

Risk of loss of confidentiality

There is some risk that health information collected as part of this study could be seen by unauthorized individuals. Every effort will be made to minimize this risk and protect subject confidentiality. Electronic data will be housed in the REDCap data management system.

REDCap is protected via Secure Sockets Layer (SSL) encryption that provides access restriction options. Exported data from REDCap will be stored on a secure password-protected server behind the BMC firewall. Source and CRF binders will be stored in a double-locked area that is accessible to only study staff. Subjects will be assigned a study identification number and this will be used to code any forms that do not require the subject's direct identifiers (e.g., consent form, laboratory results, and contact information). A linking key that associates study ID with direct identifiers will be stored in a double-locked cabinet accessible only by study team members. Data will be stored on a password-protected computer accessible only to the study team. Video of subjects during the drinking session will be stored on an encrypted drive with password protection. Video files will be deleted at the end of the study. All study staff will receive appropriate training for the protection of human subjects (NIH Protecting Human Research Participants, CITI Training). A certificate of confidentiality will be sought to protect subjects from disclosure under court order or subpoena.

Psychiatric risk

We do not anticipate that study procedures will have risk for psychiatric problems. Although we are excluding people with suicidality, it is possible that subjects will identify suicidal ideation or behavior either in screening or during the study. To minimize the risk of worsening suicidal thoughts and behaviors we will monitor suicidal thoughts and behaviors using the Columbia-Suicide Severity Rating Scale and the MINI Neuropsychiatric Interview. Subjects with a MINI suicidality score greater than 8 (low risk) will be excluded. Subjects who report any active suicidal thoughts or behavior as measured the C-SSRS will be excluded from participation. In addition to excluding active suicidality, the MINI will be used to rule out subjects who have psychiatric conditions that may increase the risk of the occurrence of suicidal thoughts or behavior (e.g., major depression, bipolar disorder). Assessment and scoring of suicide rating scales will be conducted in real-time while the subject is present. Suicidality will be assessed by trained clinical staff including study MDs, a psychologist, a nurse, and a mental health counselor. If subjects are found to be at risk for self-harm, study staff will work with the subject to develop a safety plan that could include escorting the subject to the BMC ED or calling BEST.

6.2 Potential Benefits

Calibration Study of a Wearable Noninvasive Blood Alcohol Monitor

Final V1.8 4.24.19

Although there is no potential direct benefit to participation, this study presents a strong potential for benefit to science. There are very few objective measures of alcohol consumption that can be used to determine outcomes in clinical trials for people with alcohol use disorder. Among the objective measures that are available, data about drinking is limited with regard to accurate measurement quantity and frequency of consumption. A wearable wristwatch that accurately measures BAC could be used to calculate the timing, frequency, and quantity of drinking as a continuous measure throughout an alcohol treatment study. This device also has significant potential value as a consumer device that could be used as a tool to help people achieve a goal of less risky drinking.

6.3 Analysis of Risks in Relation to Benefits

The most significant risk of this study is consuming alcohol. We have chosen a dose that is consistent with the baseline drinking of our targeted sample, and we have included appropriate protections to safeguard the well-being of our subjects. With the protections we have in place for all the potential risks in this study, we believe the risks of this study are well minimized. The study holds significant promise for helping to develop new technology that could be used in both clinical trials and the consumer market. We believe the risk/benefit ratio is favorable.

7 Study Subject Selection

7.1 Subject Inclusion Criteria

In order to be eligible to participate in this study, an individual must meet all of the following criteria:

1. 21-55 years of age.
2. Can provide proof of age with state or federal picture ID.
3. Consumes an average of ≥ 7 standard drinks per week (women) or ≥ 14 drinks per week (men) over the 28 days prior to consent.
4. Has consumed at least 4 standard drinks on a single day on at least two days in the past 28 days prior to consent.
5. Has a BAL = 0.000 at time of consent.
6. Is able to understand and provide written informed consent.
7. Body weight ≥ 120 lbs and ≤ 250 lbs
8. Subjects can speak and understand English

7.2 Subject Exclusion Criteria

An individual who meets any of the following criteria will be excluded from participation in this study:

1. Currently seeking treatment for alcohol problems or purposefully abstaining from alcohol in an attempt to cut back or quit drinking.
2. Clinical Institute Withdrawal Assessment at ≥ 10 .
3. Meets DSM-5 diagnosis of current major depression, bipolar disorder, schizophrenia, bulimia/anorexia, dementia, or a substance use disorder other than alcohol, nicotine, marijuana, or caffeine

Calibration Study of a Wearable Noninvasive Blood Alcohol Monitor

Final V1.8 4.24.19

4. If female, pregnant or nursing.
5. If female, does not agree to use an accepted form of birth control
6. Has medical or mental condition for which further alcohol exposure at the planned dose range would be contraindicated.
7. Taking medication for which drinking would be contraindicated.
8. Clinically significant abnormal ECG.
9. AST or ALT $\geq 3x$ the upper limit of normal.
10. Current risk of suicidality.
11. Has taken medications that are used to treat AUD in the past 90 days.
12. Has received alcohol counseling or other non-pharmacologic intervention to treat AUD in the past 90 days.
13. Has urine toxicology results positive for cocaine, opioids, amphetamines, buprenorphine, methadone, or methamphetamines.
14. Smokes greater than 5 cigarettes per day.
15. Unable to comfortably abstain from nicotine for a period of 8 hours.
15. Wearing cologne, perfume, aftershave or any other scented oil or alcohol-based beauty product on the day of the Alcohol Lab Visit.
16. Has dietary restrictions that would preclude participating.

8 Study Intervention

This is a non-interventional study.

9 Study Procedures

Study Overview: Each subject will complete 4-5 clinic visits over a period of up to 9 months of participation. Study participation is comprised of a baseline assessment, Phase I BAL calibration session, Phase II eligibility determination session, and Phase II BAL validation session.

Baseline assessment

Consenting subjects will undergo a general medical screen, including medical history physical examination. Drinking will be assessed using the TLFB [16], alcohol withdrawal using the Clinical Institute Withdrawal Assessment [17], and suicidality using the Columbia-Suicide Severity Rating Scale (C-SSRS) [18]. Exclusionary mental health conditions will be assessed using the MINI Neuropsychiatric Interview for DSM-5 [19]. Subjects will undergo urine toxicology and a urine pregnancy test for women of child bearing age. The baseline assessment may be completed in one or two visits.

Phase I BAL Calibration session:

Subjects will return to the laboratory within 14 days after completion of the baseline assessment to complete the Phase I BAL calibration session. For safety reasons, subjects will be asked to arrange transportation plans for this study visit. The alcohol lab visit is divided into four phases: 1) Screening, 2) Zero BAL observation, 3) Alcohol Administration, and 4) Observation.

1) *Screening.* Eligibility to continue in the study will be confirmed in a brief screening session. Subjects will undergo vital signs, alcohol breath test, urine drug screening, assessment of concomitant medications, assessment of alcohol withdrawal, urine pregnancy testing (for women), adverse event assessment, suicidality screening, and assessment of drinking since the

Calibration Study of a Wearable Noninvasive Blood Alcohol Monitor

Final V1.8 4.24.19

baseline. Blood alcohol level must be 0.000 to continue with the study procedures. Subjects will be excluded if urine toxicology results positive for cocaine, opioids, amphetamines, buprenorphine, methadone, or methamphetamines. Subjects will also be excluded if any concomitant medications that present safety issues for drinking have been started since the baseline assessment. Subjects will be excluded if the CIWA ≥ 10 or if the C-SSRS indicates any current suicidal ideation or behavior.

2) *Zero BAL observation.* Subjects will be escorted from the Clinical Studies Unit to the General Clinical Research Unit (GCRU) for the remainder of the alcohol lab visit. The room in the GCRU that will be used is carpeted and furnished with a lounge chair, side table, table lamp and television which allows access to popular streaming entertainment (e.g., Netflix, YouTube, and HBO-GO). A small unobtrusive camera is mounted in one corner to allow for monitoring without study staff being present in the room. During the Zero BAL observation period (and all subsequent phases in the GCRU) study staff and subjects will be instructed not to use any alcohol-based sanitizing hand cleaners due to the potential for interference with the BAL wristwatch sensor. During the Zero BAL session study staff will fit the BAL wristwatches on subjects and begin a 1-hour period of baseline monitoring of a zero BAL. This observation period will be used to demonstrate that the BAL wristwatches do not provide false positive readings under zero BAL conditions. Study staff will measure BAL every 15 minutes during this 60-minute observation period using a breathalyzer. Subjects will have access to streaming entertainment during this period, but will be asked to limit use personal electronics for the duration of the zero BAL session.

3) *Alcohol Administration.* After 60 minutes of Zero BAL observation the drinking self-administration session will begin. At the start of the alcohol administration session the subject will be given a pre-determined volume of alcohol designed to raise BAL to 0.05 g/dL. The volume of alcohol will be calculated using an online tool developed by UW-Madison (<http://dionysus.psych.wisc.edu/WebCMS/baccalc.htm>) based on a formula described by Watson⁵⁹. The hour-long drinking session will be followed by a five hour observation period to ensure that subject reach peak TAC. Blood alcohol level will be measured simultaneously using the transdermal sensors and the breathalyzer for the duration of the drinking period and observation period. Breathalyzer readings will be taken every 15 minutes during the entire experiment and transdermal sensors will log data continuously. To ensure residual alcohol in subjects' mouths does not provide a false breath alcohol reading, subjects will rinse their mouth twice with water after consuming a saltine cracker prior to each breathalyzer given while the subject is consuming alcohol. Subjects will have access to streaming entertainment during this period, but will be asked to not use personal electronics for the duration of the self-administration session. This drinking session will be video recorded to confirm exact times of BAL readings taken with the breathalyzer. Subjects will remain in the laboratory until their BAL, as measured by breathalyzer, reaches 0.04 g/dL or less.

4. *Observation.* Subjects will remain in the drinking lab for five hours of observation following alcohol administration. Breathalyzer readings will be taken every 15 minutes during the observation and transdermal sensors will log data continuously. Data from this observation will be used to develop a model that adjusts for the lag in peak TAC relative to measured BAL using a breathalyzer. Subjects will continue to have access to streaming entertainment and will also

Calibration Study of a Wearable Noninvasive Blood Alcohol Monitor

Final V1.8 4.24.19

have access to any personal electronic devices for this phase. Subjects will consume crackers and water just prior to the first breathalyzer reading during this phase. This observation period will be video recorded to confirm exact times of BAL readings taken with the breathalyzer. Subjects will be monitored during the observation until their blood alcohol level is ≤ 0.0 g/dL and they are not behaviorally impaired to leave. Four hours after consuming alcohol subject will be given a light meal that is approximately 375 calories. Study staff will assess intoxication, sedation, and adverse effects during this observation period. Subjects will also have access to snacks (e.g. chips, granola bars) and non-alcoholic beverages if the time needed to reach ≤ 0.04 g/dL exceeds the 5-hour observation period. Subjects will be required to have a plan for transportation home that does not involve driving or riding non-motorized transportation (e.g., bike, scooter).

Phase II eligibility determination session

Once all subjects have completed phase I of the study and the model for adjusting TAC readings has been developed, subjects will be invited back to the lab to complete phase II of the study. Eligibility will be re-assessed to ensure subject safety prior to completing the second drinking lab (see appendix A for schedule of testing events).

Phase II BAL validation session

Within 14 days of subjects completing the Phase II eligibility Determination session, subjects will return to the clinic to complete the Phase II BAL validation session. This second alcohol lab visit is divided into the same four phases as the Phase I BAL calibration session: 1) Screening, 2) Zero BAL observation, 3) Alcohol Administration, and 4) Observation. The procedures for this second alcohol lab session are the same with a few exceptions:

- 1) Subjects will be wearing second generation wristwatch sensors.
- 2) TAC readings will be converted into estimated breathalyzer BAL readings based on the model developed in Phase I.
- 3) The observation period will last only 3 hours (or longer if needed for BAL to reach ≤ 0.04 g/dL).

If a subject completes Phase I and is unable to complete Phase II for any reason, replacement subjects will be recruited to complete Phase I and II consecutively. It is estimated that 36 subjects will be consented to yield 12 subjects that will complete Phase I and 9 subjects that will complete Phase II. Based on past experience with subject attrition, it is estimated that 33% of the Phase I subjects will be replaced at the time of phase II. Given the sample size requirements for this study are 9 subjects to complete both trials, the total sample size is estimated to be 12 subjects taking into account the possibility that three subjects will be lost to follow-up between trials one and two. If subjects are lost, when these subjects are replaced they will complete both the calibration session and validation session over the period of approximately 60 days.

Subject compensation

Subjects will be compensated up to \$340 for completion of all study activities. In addition to reimbursements for each study visit, subjects who complete all study visits will receive a completion bonus at the end of the study. If at any time subjects are discontinued from the study during a visit, subjects will be paid a portion of the payment based on time completed (e.g., 1

Calibration Study of a Wearable Noninvasive Blood Alcohol Monitor

Final V1.8 4.24.19

hour completed of two-hour visit = 1/2 of payment). Note there is an exclusion for payment due to UDS+ at the baseline.

Subjects will receive the following reimbursements:

Baseline assessment	\$40
Phase I BAL Calibration session	\$100
Phase II eligibility determination session	\$40
Phase II BAL validation session	\$100
Completion Bonus	\$60

10 Assessment of Safety and Data Safety Monitoring Plan (DSMP)

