3.1 Background Information

The goal of this study will be to continue development and commercialization of a new noninvasive transdermal alcohol monitor developed by KWJ Engineering, Inc. The wrist-mounted transdermal ethanol measurement system being studied in this proposal is part of the modern trend toward wearable and noninvasive measurements. In recent years there has been a growing trend in science and technology toward developing noninvasive on-body, continuous measurements in the management of chronic disease, monitoring the elderly, diagnostic sensing and other biomedical applications [1-7]. Stretchable and flexible materials for dermal sensors are emerging, as are new approaches to making physical and chemical measurements noninvasively on the skin [8-11]. KWJ engineering is an industry-leading manufacturer of monitoring sensors, instruments, and gas sensors designed to reduce risks to health, safety, and security in commercial and consumer environments. KWJ has recently received an SBIR phase II award from NIAAA to continue efforts to develop a wearable transdermal sensor that monitors Blood Alcohol Level (BAL) in real-time. The monitor is based on the KWJ Engineering's printed electrochemical gas sensor that is able to detect ethanol concentrations in the skin. This ethanol sensor is a very small, ultralow power, and highly sensitive device with very low interferences. In previous studies leading up to the SBIR award, KWJ Engineering has demonstrated stable and sensitive measurement of ethanol across human skin surrogate membranes. This was accomplished with an initial prototype wristwatch device that included the ethanol sensor and circuitry for performing the measurement and converting data for wireless communication to a computer. Raw transdermal ethanol concentrations were calibrated to blood alcohol values using standardized ethanol solutions as a surrogate for blood alcohol concentration (BAC). KWJ has demonstrated a high degree of reproducibility in measurement sensitivity across several watch format devices.

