Predicted BAL that will be determined from TAC data are expected to be equivalent to BrAc concentrations. We, therefore hypothesize that there will be a strong correlation between BAL and BrAc measurements obtained at the same time points for the individual subjects. The reference breathalyzer response is known to be linear over the range of expected blood alcohol levels in the study [23]. Therefore, the breathalyzer and predicted BAL values are expected to be linearly related to each other. To confirm the hypothesis that these values are highly linearly related an analysis will be conducted in which repeated measures correlation coefficient (rcmm) between BrAc and BAL will be obtained. In contrast to a simple correlation analysis of data in which repeated measures collected from individual subjects are used, here will be no violation of the assumption of independence of observations when rcmm values are utilized as the measure of the extent of correlation between these values [Bakdash and Marrusich, 2017].

Calibration Study of a Wearable Noninvasive Blood Alcohol Monitor
Final V1.8 4.24.19

Data obtained in the validation phase of this study will be analyzed using the proc glm procedure for SAS 9.4. This data will include values for individual subjects obtained for each time-point at which BrAc measurement were made and corresponding predicted BAL values determined for these subjects. This data will be analyzed using following general linear model:

BAL= BrAc sub

This model is equivalent to an analysis of covariance model in which subjects (sub) are a covariate. This model will allow for the determination of whether BrAc and BAL values are significantly related to one another. The correlation coefficient [rcmm] for relationship between BAL and BrAc will be determined using the following equation first mentioned by Bland and Altman [24] with sum of squares values being obtained from the results of our glm analysis: $rcmm = \text{square root} [\text{Sum of Squares BAL} / (\text{Sum of Squares BAL} + \text{Sum of Squares Residual})]$

Since both BrAc and BAL measurements are hypothesized to be linear, the rcmm value is expected to be >0.80 with high correlation power. The statistical null hypothesis is that the predicted BAL measurements are not related to the standard breathalyzer measurements. The study is designed to maintain a probability of Type I and Type II error rates with respect to the null hypothesis at $p<0.05$.

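### Phase II applies the Phase I conversion model to second-generation watches with no described bridging, and the planned correlations cannot show that predicted BAL equals breath alcohol on the new hardware

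*Combined protocol and SAP*

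**What the plan says.** Section 9 (Phase II BAL validation session) introduces the second drinking session with "The procedures for this second alcohol lab session are the same with a few exceptions". The first exception listed is "Subjects will be wearing second generation wristwatch sensors". The second is "TAC readings will be converted into estimated breathalyzer BAL readings based on the model developed in Phase I". The Phase I sensor is not named.

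Section 4.2.1 sets the endpoint: "The primary outcome is the correlation in estimated BAL as measured by the breathalyzer and the wristwatch sensor during the second alcohol self-administration trial". Section 12.1 analyses it with a general linear model, predicted BAL = BrAC + subject, and forms the repeated measures correlation (rcmm) from the sums of squares. The null is one of no association: "The statistical null hypothesis is that the predicted BAL measurements are not related to the standard breathalyzer measurements". Section 12.2 says the device is useful only if r exceeds 0.9. The formal Cmax and Tmax analyses in Section 12.1, and the AUC and Cmax fallback in Section 12.2, are Pearson correlations.

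The stated ambition is larger than association. The synopsis aims to test the accuracy of the watch against breath testing, and Section 12.1 expects predicted BAL to be equivalent to BrAC.

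Two descriptive checks bear on level. Section 12.1 plans to look for differences in sensitivity and to examine each subject's curves for systematic differences in Cmax and Tmax. The zero-BAL hour in Section 9 looks for false positives when no alcohol is present.

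**The concern.** A model fitted to one sensor carries that sensor's gain, offset and response time. If the second-generation watch differs in any of these, the model is applied to a signal it was not fitted to. The documents describe no side-by-side wear, no bench comparison of generations and no refitting.

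This affects what the trial can conclude in two ways. A high correlation would not show that the predicted values are at the right level, because a correlation ignores level and scale. A low correlation, or a visible shift in the curves, could not be assigned to the hardware, to the model, or to the months between sessions. The first matters more, because the plan wants to speak of accuracy and equivalence.

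**Working it through.** **Inputs from the plan.** The rcmm formula and null hypothesis are in Section 12.1, and the r > 0.9 criterion is in Section 12.2. The target peak is 0.05 g/dL (Sections 5 and 9). Power is given for 9 subjects with 21 points and 5 subjects with 10 points, and for a Pearson r of 0.8 with n = 9 (Section 12.2). Alpha is 0.05; sidedness is not stated, so two-sided is assumed.

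**The plan's own figures reproduce.**
- Pearson, r = 0.8, n = 9: 400,000 simulated t-tests give power 0.820, against the stated 0.82.
- rcmm, using the plan's degrees of freedom: (9 − 2)(21 − 1) = 140 and (5 − 2)(10 − 1) = 27. Power at r = 0.8 is above 0.9998 in both cases, against the stated > 0.995.

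These powers are for rejecting r = 0. They say nothing about level.

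**Why rcmm ignores a common gain or offset.** Let P be predicted BAL and P′ = a + bP with b > 0, the same a and b for every watch.
1. Centring within subject removes a and leaves b(P − subject mean).
2. The sum of squares for the BrAC term and the residual sum of squares are both multiplied by b².
3. The ratio SS / (SS + SS residual), and so rcmm and its p-value, do not change.

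The same holds for a Pearson correlation of Cmax, and of AUC over a common time window. Tmax does not move at all.

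**From raw TAC to predicted BAL.** If the conversion is linear, P = c + d·TAC, a sensor gain g gives c + d·g·TAC = c(1 − g) + gP. This is again a + bP. The documents do not give the form of the conversion, so linearity is an assumption.

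**Size, on assumed gains and c = 0.** The documents give no gain difference.
- 20% lower: 0.050 × 0.8 = 0.040 g/dL.
- 10% to 30% either way: from 0.050 × 0.7 = 0.035 to 0.050 × 1.3 = 0.065 g/dL.

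**Illustration with the plan's model.** Assumed: 9 subjects, 16 readings at 15-minute spacing over 4 hours, peak about 0.05 g/dL, noise SD 0.006 g/dL, 2,000 runs.

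| Common gain | Mean rcmm | Cmax Pearson r | Mean bias (g/dL) | Mean Cmax difference (g/dL) |
|---|---|---|---|---|
| 0.50 | 0.911 | 0.823 | −0.014 | −0.024 |
| 0.75 | 0.911 | 0.823 | −0.007 | −0.011 |
| 1.00 | 0.911 | 0.823 | 0.000 | +0.003 |
| 1.25 | 0.911 | 0.823 | +0.007 | +0.016 |
| 1.50 | 0.911 | 0.823 | +0.014 | +0.029 |
| 2.00 | 0.911 | 0.823 | +0.028 | +0.055 |

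A watch reading half or double has the same mean rcmm, above 0.9, as a correct one. In a single simulated data set the slope of predicted BAL on BrAC moved from 0.50 to 1.50 while rcmm stayed at 0.9096; adding an offset of 0.02 g/dL changed neither.

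**Where the correlations do react.**
- Gains that vary between watches: at a CV of 10%, 20% and 30%, rcmm falls from about 0.910 to 0.906, 0.894 and 0.877. The Cmax Pearson r falls from about 0.81–0.82 to 0.68, 0.49 and 0.37.
- Extra uncorrected lag, without noise: rcmm is 0.89 at 15 minutes and 0.64 at 30 minutes.

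**The case against.** The strongest reply is that the plan does look at level. The Section 12.1 inspection of sensitivity and of systematic Cmax differences is aimed at just such a case as 0.050 reading as 0.040. The Tmax comparison bears on response time, and the zero-BAL hour, repeated in Phase II, bears on a positive offset. This stands: a reader might infer that the design is blind to a hardware shift, and it is not. But the inspection has no estimate, interval or limit, so it cannot support a statement of equivalence. The zero-BAL hour says nothing about gain.

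The invariance also has conditions, and these stand too. It needs a linear conversion and a shift common to all watches. Section 12.2 contemplates using only pairs in which both devices read above zero, so an offset or a loss of sensitivity could change which pairs enter, and hence rcmm.

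Updating a prototype between phases is normal in device development. Section 4.1 asks about the sensor against the breathalyzer and does not ask which component causes an error. Section 5 allows amendment for methodology issues before Phase II is completed. So testing the new watch is a defensible choice. What it needs is a clear label and a measure of agreement.

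Finally, correlation would not be agreement even with identical watches. That is true. The change of sensor adds a specific reason why the level may move between calibration and validation.

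**Conclusion.** The point holds in this form: with no described bridging, the planned correlations and the r > 0.9 criterion cannot show that predicted BAL is equivalent to BrAC on second-generation hardware. For a common shift through a linear conversion the invariance is exact at any size of shift; the 20% example (0.050 read as 0.040 g/dL) is an assumption. The plan's descriptive checks could reveal a shift, but could not quantify it against a limit or separate hardware from model error.

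Two stronger readings are not supported. One is that a gain shift is the likely result of the new sensor: the documents do not say what differs between generations, and the earlier generation in Phase I is itself inferred from the list of exceptions. The other is that no hardware change would register in the primary result: extra lag, and gains that differ between watches, do lower rcmm.

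The trial can run as planned. What is at risk is any claim of accuracy or equivalence drawn from it.

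**What to change.** **In Section 12.1, for the Phase II data, add:**
- The slope and intercept relating BrAC and predicted BAL, with the direction fixed in advance. The planned model already yields the slope of predicted BAL on BrAC. The reverse regression is flattened by sensor noise: in the single simulated data set at gain 1 its within-subject slope would be 0.9096² / 1.001 ≈ 0.83 although nothing is miscalibrated.
- The mean difference, overall and at Cmax, with limits of agreement suited to repeated readings. The overall difference should lead, because the maximum of noisy readings overshoots (+0.003 g/dL at gain 1 in the table).
- Confidence intervals that account for clustering by subject. A simple choice is one slope and one mean difference per subject, with a t-interval on 9 − 1 = 8 degrees of freedom.
- A rule that these are reported with rcmm, against a limit the sponsor sets in advance, before accuracy or equivalence is claimed.

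**In Section 9,** state the sensor generation for every session. This includes the Phase I session of late entrants, since "replacement subjects will be recruited to complete Phase I and II consecutively" leaves their calibration sensor open. Word the conclusion as applying to the Phase I model combined with second-generation hardware.

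These changes use data already planned and cost only text and analysis time.

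**Optional.** Run both generations on the developer's ethanol standards before Phase II. Section 3.1 shows the method exists ("Raw transdermal ethanol concentrations were calibrated to blood alcohol values using standardized ethanol solutions"). The cost is a small amount of bench work, and the result may not carry over fully to skin: the earlier work used surrogate membranes, and Section 12.2 says sensitivity in humans is unknown. Replacement subjects wearing both generations would be a bonus at most. Section 9 implies three (12 − 9) or about four (0.33 × 12 = 3.96) such subjects, but their number and timing depend on dropout.
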